2. SYNOPSIS

Trial Title	Fully hybrid 18F-PSMA PET/MRI as one-stop approach for the diagnosis of clinically significant prostate cancer	
Protocol Acronym/Number	RF-2021-12372278	
Protocol Version and Date	v2.0, 30 GEN 2023	
EudraCT number	NA	
Sponsor	IRCCS Ospedale San Raffaele [name]	
Funding Source(s)	Italian Ministry of Health	
Principal Investigator	[name], U.O. of Nuclear Medicine	
Trial Description	
This project aims to evaluate the role of fully hybrid PET/MRI with 18F-PSMA and multiparametric MR imaging (mpMRI) as one-stop approach for the diagnosis of clinically significant prostate cancer (csPCa).
 
Our main hypothesis is that adding 18F-PSMA PET to mpMRI prior to biopsy, will reduce the number of false negative findings, while at the same time, allowing also to reduce the number of unnecessary prostate biopsies in patients with low-risk, clinically indolent PCa.
	
	Primary	Secondary
Objectives	To assess the accuracy and the predictive value of fully hybrid 18F-PSMA PET/MRI for the diagnosis of csPCa	
 1) To compare the proportion of csPCa missed by 18F-PSMA PET scan or mpMRI alone 2) To report the reduction in the detection of clinically insignificant PCa when combining mpMRI and 18F-PSMA PET, and consequently the proportion of unnecessary biopsies potentially spared.
Endpoints	Diagnostic accuracy measured with sensitivity, specificity, positive and negative predicted value	
 1) The number of csPCa missed by PET and MR imaging when read independently 2) Only in patients with positive mpMRI and negative 18F-PSMA PET: The proportion of clinically insignificant PCa
Time point(s)	day 0: 18F-PSMA PET/MRI day 90 (+/- 90): prostate biopsy	
Phase	Phase II	
Trial Design	Monocentric, single-arm, prospective	

Trial Population	Men with clinical suspicion of csPCa.
Inclusion Criteria	1) Men at least 18 years of age referred with clinical suspicion of prostate cancer candidate for prostate biopsy 2) Feasibility to undergo all procedures listed in protocol 3) Ability to provide written informed consent
Exclusion Criteria	1) Prior diagnosis of prostate cancer 2) Contraindication to MRI (e.g. claustrophobia, pacemaker, estimated GFR lower or equal to 50mls/min) 3) Contraindication to prostate biopsy
Intervention(s)	
IMP(s)	18F-PSMA, 4 MBq/Kg, intravenous administration
NIMP(s)	Not applicable.
Other intervention(s)	Prostate biopsy guided by imaging findings
Comparator	Not applicable.
Safety Criteria	Patients' compliance.
Efficacy Criteria	Diagnostic accuracy
Sample Size	167 patients, all enrolled at OSR
Statistical Design	Diagnostic accuracies of 18F-PSMA PET and mpMRI will be calculated by means of sensitivity: true positive/(true positive + false negative); specificity: true negative/(false positive + true negative); PPV: true positive/(true positive + false positive); and NPV: true negative/(true negative + false negative) using the prostate biopsy result as reference standard
List of Enrolling Sites (if applicable)	Not applicable.
Duration of the Trial	Duration of enrollment: 27 months Duration of treatment: two hours per patient (over 27 months)

Duration of total follow-up: NA (after biopsy there will not be further visits)
Duration of total trial period: 36 months

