6. OBJECTIVES AND ENDPOINTS

Objectives	Endpoints	Time point(s)
Primary Objective To assess the accuracy and the predictive value of fully hybrid ^{18}F -PSMA PET/MRI for the diagnosis of csPCa	Primary Endpoint Diagnostic accuracies of ^{18}F -PSMA PET and mpMRI will be calculated by means of sensitivity: true positive/(true positive + false negative) and specificity: true negative/(false positive + true negative) using the prostate biopsy result as reference standard.	PET/MRI examination at day 0, and biopsy at day 1-30 (within a month from imaging study)
Secondary Objectives To compare the proportion of csPCa missed by ^{18}F -PSMA PET scan or mpMRI alone	Secondary Endpoints The proportion of csPCa (defined by analysis of prostate biopsy cores, ISUP grade equal or higher than 2) missed by PSMA PET scan or mpMRI alone will be calculated.	PET/MRI examination at day 0, and biopsy at day 1-30 (within a month from imaging study)
Exploratory Objectives To assess the proportion of unnecessary biopsies potentially spared	Other Number of clinically insignificant PCa (ISUP grade 1) identified combining mpMRI and ^{18}F -PSMA PET.	PET/MRI examination at day 0, and biopsy at day 90 (+/-90)

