Patients with both negative mpMRI and 18F-PSMA PET scan will receive a 12-core TRUS-Bx. Patients with only positive mpMRI will receive MRI-TBx and 12-core TRUSBx. Patients with only positive 18F-PSMA PET will receive 18F-PSMA PET-TBx and 12-core TRUSBx. MRI-TBx will be performed by means of a fusion software-assisted approach using the Biojet system taking 4 cores in any mpMRI suspicious areas. PSMA PET-TBx will be performed taking 4 cores in the area of the prostate showing an increased tracer uptake. All prostate biopsy specimens will be evaluated by fully dedicated uro-pathologist.

In order to calculate accuracy, sensitivity, specificity, positive predictive value and negative predictive value of 18F-PSMA PET/MRI for the identification of csPCa, 18F-PSMA PET/MRI findings will be correlated with histopathological samples gathered with prostate biopsy.

The proportion of csPCa missed by PSMA PET scan or mpMRI alone will be then calculated.

In order to study the proportion of unnecessary biopsies that could be spared by adding 18F-PSMA PET to mpMRI in the triage phase, only patients with positive mpMRI and negative 18F-PSMA PET scan will be considered for the analysis and the proportion of clinically insignificant PCa detected in this subset of patients will be assessed. In this way we will identify proportion of unnecessary prostate biopsies that could have been spared, thus reducing overdiagnosis.

Furthermore, the potential role of quantitative PET and mpMRI parameters in identifying csPCa will be investigated. Specifically, recently emerging radiomic features will be evaluated, together with PET- and MRI-derived quantitative conventional imaging parameters, and regression analyses will be used for evaluating their role in predicting histopathological data. To assess the diagnostic performance of PET and MRI parameters, ROC curve analysis will be performed to select optimal cut-offs in predicting the presence of csPCa as defined by cytological examination and the corresponding diagnostic accuracy will be computed (more detailed information in the section "Statistics" of this protocol). No interim analyses are planned.

The following measures will be taken in order to minimize the risk of bias:

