10.6. Preparation, Administration and Accountability of the Trial Treatments

Radiotracer synthesis: 18F-PSMA synthesis is performed using an automatic synthesis module (NEPTIS) through the incorporation of 18F (produced by the IBA 18 MeV cyclotron) in a PSMA 1007 precursor molecule; after formulation and sterilization on a 0.22 µm filter membrane, quality control is performed to evaluate the chemical, radiochemical, radionuclidic and microbiological purity of the final product in compliance with the monograph of Eu. Ph. 3116.

PET/MR acquisition protocol: PET/MRI will start approximately 90 minutes after intravenous administration of 4 MBq/Kg of 18F-PSMA. A PET/MR total body acquisition and a high statistics pelvic PET simultaneously acquired to mpMRI will be performed. Using 3 Tesla PET/MR system the endorectal coil is not needed for the MR acquisition thus increasing patient compliance.

MpMRI protocol will follow ESUR guidelines: axial T2 weighted sequence with large field of view (FOV), axial and sagittal T2 weighted sequence with small FOV, DWI sequence with small FOV $b = 50, 800, 1400; 2000 \text{ s/mm}^2$ and ADC maps, T1-Lava Flex sequence of the pelvic region pre-contrast and post-contrast, a high temporal resolution T1 perfusion sequence after IV injection of 0.1 mmol/kg bolus of gadobutrol at a flow rate of 3.5 mL/s.

PET/MRI qualitative analysis: images will be evaluated by expert Nuclear Medicine and Radiologist physicians blinded to each other on the Advantage Workstation (AW, General Electric Healthcare, Waukesha, WI, USA) where PET, MRI and fused PET/MRI images can be visualized in axial, coronal and sagittal planes. Focal uptake of 18F-PSMA higher than background and not associated with physiologic uptake was considered positive. For mpMRI, T2W morphological, diffusion (DWI) and perfusion (DCE) sequences will be used to define lesions according to PIRADS v. 2.1 classification (7). Lesions classified as PI-RADS ≥ 3 on mpMRI images and/or showing increased 18F-PSMA uptake on PET, will be considered positive for csPCa.

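### The endpoint for secondary objective 2 is a share within mpMRI-positive/PET-negative men, which neither determines nor reliably tracks the reduction and the spared biopsies that the objective asks for

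*Combined protocol and SAP*

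**What the plan says.** The synopsis gives secondary objective 2 as "To report the reduction in the detection of clinically insignificant PCa when combining mpMRI and 18F-PSMA PET", and, following from that, the proportion of biopsies that could be avoided as unnecessary. The secondary endpoint beside it is "Only in patients with positive mpMRI and negative 18F-PSMA PET: The proportion of clinically insignificant PCa".

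Section 8 (Trial Design) confirms the restriction: "only patients with positive mpMRI and negative 18F-PSMA PET scan will be considered for the analysis". What is measured in those men is again a within-subset share of ISUP 1 disease. The section then draws the inference: "In this way we will identify proportion of unnecessary prostate biopsies that could have been spared, thus reducing overdiagnosis".

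Section 6 (Objectives and Endpoints) lists the spared-biopsy aim as exploratory rather than secondary, with a different measure: "Number of clinically insignificant PCa (ISUP grade 1) identified combining mpMRI and ^{18}F -PSMA PET". That is a count, with no mpMRI-alone comparator and no denominator.

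Section 16.1 gives formulas for sensitivity, specificity and predictive values, and a McNemar test for secondary objective 1. It gives no method for secondary objective 2.

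Two other provisions matter. Under section 8 every man is biopsied, whatever the imaging shows. And sections 8 and 10.6 call a finding positive if either modality is positive: "Lesions classified as PI-RADS ≥ 3 on mpMRI images and/or showing increased 18F-PSMA uptake on PET, will be considered positive for csPCa".

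**The concern.** A reduction is a fraction of what would have happened otherwise. Here the reference is what an mpMRI-led pathway would have detected or biopsied, so the denominator must come from all mpMRI-positive men. The endpoint divides by the discordant subset instead. It estimates P(ISUP 1 | mpMRI+, PET-), the make-up of a PET-negative result. The objective needs the reverse conditionals: P(PET- | mpMRI+, ISUP 1) for the reduction in insignificant cancer, and P(PET- | mpMRI+, no csPCa) for unnecessary biopsies spared.

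The discordant subset is the right place to count what PET would avoid. The error is to use it as the denominator as well.

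Fewer unnecessary biopsies and less detection of indolent disease form one half of the main hypothesis in the synopsis. If the result is reported as section 8 describes, the composition of a subset would be presented as a proportion of biopsies spared.

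**Working it through.** **The plan's own figure.** The documents state no number for this endpoint. The stated total of 167 reproduces: 1.96² × 0.96 × 0.04 / 0.04² = 92.2, rounded up to 93 men with csPCa; 93 / 0.56 = 166.07, rounded up to 167. It rests on sensitivity alone and does not bear on this endpoint.

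**Notation.** Among mpMRI-positive men, let M be their number and I the number with ISUP 1. Among the PET-negative men within M, let n be their number and a the number with ISUP 1.

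- Planned share: S = a / n
- Reduction in ISUP 1 detection: R = a / I
- mpMRI-led biopsies avoided: B = n / M

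Substituting a = R × I and n = B × M gives S = (R / B) × (I / M). For a given case mix I / M, the share fixes only the ratio of R to B, not the size of either.

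**Same share, different answers.** The documents give neither M nor I. Assume M = 110 and I = 20.

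| a / n | S | R = a / 20 | B = n / 110 |
|---|---|---|---|
| 2 / 5 | 40% | 10% | 4.5% |
| 4 / 10 | 40% | 20% | 9.1% |
| 8 / 20 | 40% | 40% | 18.2% |
| 16 / 40 | 40% | 80% | 36.4% |

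Other assumed totals (M = 120, I = 30; subsets of 10 to 60 men) give the same pattern: a 40% share fits R from 4/30 = 13% to 24/30 = 80%, and B from 10/120 = 8% to 60/120 = 50%.

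**How the share moves (M = 120, I = 30).**

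- Fixed n = 20 with a = 4, 8, 12: S is 20%, 40%, 60% and R is 13%, 27%, 40%, while B stays at 17%. The share rises with the ISUP 1 cancers avoided.
- Fixed a = 8 with n = 10, 20, 40: S is 80%, 40%, 20%, while B is 8%, 17%, 33%. The share falls as more biopsies are spared.
- When a and n scale together, S does not change (table above).

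**Ranking can reverse (M = 110, I = 20).** 6/10 gives S = 60% with R = 6/20 = 30%; 14/40 gives S = 35% with R = 14/20 = 70%. A milder pair does the same: against 6/10, 8/20 has a lower share (40%) and a larger reduction (8/20 = 40%).

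**How extreme is the top row?** At 56% prevalence, 0.56 × 167 is about 94 men with csPCa. If mpMRI flags 80% to 90% of them (assumed), 75 to 85 of the 110 have csPCa, leaving 110 - 20 - 75 = 15 down to 110 - 20 - 85 = 5 benign men. The 16/40 row has 24 PET-negative men without ISUP 1, so at least 24 - 15 = 9 to 24 - 5 = 19 of them would have csPCa. That is possible but extreme. Without this row, a 40% share still fits R from 10% to 40% and B from 4.5% to 18.2%.

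**Patients or cancers as denominator.** The wording does not say which. Take the M = 120 subsets with 4, 8, 16 and 24 ISUP 1, and assume 1, 2, 4 and 6 csPCa. The cancer-based share is 4/5 = 8/10 = 16/20 = 24/30 = 80% throughout. The mismatch holds either way.

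**Positivity rule.** If either modality suffices for a positive result, every mpMRI-positive man remains positive when PET is added. Under that rule no mpMRI-led biopsy is spared, whereas the section 8 analysis presumes that mpMRI-positive/PET-negative men would be spared.

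**The case against.** The strongest objection is that the text names no denominator. On grammar alone, the phrase in section 8 could mean the fraction of all insignificant cancers that fall in the subset, which is close to R. The preceding clause defeats this: if only the discordant men enter the analysis, insignificant cancers outside the subset cannot be in the denominator. What stands is that the text does not choose between patients and cancers within the subset.

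A second objection is that nothing is lost. This largely stands. All men are biopsied, and the planned mpMRI predictive value and specificity already use all mpMRI-positive men and all mpMRI-positive men without csPCa. Only the ISUP 1 total among mpMRI-positive men needs an extra tabulation. A reader might infer that the trial cannot answer the question; the documents do not support that. The defect is in the specified measure and in the inference drawn from it.

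A reader might also infer that the share is unrelated to what PET would avoid. That is too strong. Its numerator is exactly the number of ISUP 1 cancers avoided, and it does move, as the working shows.

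Finally, the synopsis ties unnecessary biopsies to men with indolent cancer, so counting benign results widens the protocol's concept. That is fair, and the choice should be stated openly.

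**Conclusion.** The point holds. The planned share neither determines nor reliably tracks the reduction in insignificant-cancer detection or the biopsies spared, and the inference in section 8 is wrong. Neither section 6 nor section 16.1 repairs it.

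With 110 mpMRI-positive men and 20 ISUP 1 assumed, a 40% share fits a 10% to 80% reduction and 5% to 36% of mpMRI-led biopsies avoided, the upper end being extreme. The percentages rest on those assumed totals; the mismatch is algebraic and does not. The primary endpoint is unaffected. A named secondary objective is left without a measure that answers it, so the plan should be changed.

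**What to change.** Amend the synopsis and sections 6, 8 and 16.1. For a hypothetical pathway in which mpMRI-positive/PET-negative men would not be biopsied, report each of these with an exact 95% confidence interval:

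1. mpMRI-positive/PET-negative men with ISUP 1, divided by all mpMRI-positive men with ISUP 1. Label this the reduction among mpMRI-positive men. Report ISUP 1 found in mpMRI-negative/PET-positive men separately, because a combined pathway could add these.
2. mpMRI-positive/PET-negative men without csPCa, divided by all mpMRI-positive men without csPCa, stating that benign results count as unnecessary biopsies. Also give all mpMRI-positive/PET-negative men divided by all mpMRI-positive men.
3. Alongside these, the significant cancers that would be missed: mpMRI-positive/PET-negative men with csPCa, divided by all mpMRI-positive men with csPCa.

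Keep the within-subset share only as a description of the histology behind a PET-negative result. Give the aim one level (secondary in the synopsis, exploratory in section 6) and one definition. Reconcile the either-modality positivity rule in sections 8 and 10.6 with the sparing analysis in section 8. These are definitions for analysis and do not say who should be biopsied.

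The cost is wording and a few tabulations, with no new data. Some intervals will be wide because the ISUP 1 denominator is small: 8/20 gives 40% with an exact 95% interval of 19% to 64%.

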7.2. Safety Criteria

A large amount of evidence shows that ¹⁸F-PSMA is well tolerated, and it is not associated with serious adverse events (SAE) (6). Drug's reaction could occur, in a very small percentage of the population as it is reported in the normal clinical practice. Patients presenting contraindication to PET/MRI examination will be excluded from the study a priori. More details on this can be found in the section "Exclusion criteria" of this protocol.

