10.7. Compliance with Trial Treatment

All patients that will complete PET/MRI examination and will undergo prostate biopsy will be considered compliant with the clinical trial. A through database containing all relevant information for this study will be generated and patients that fail to complete the study procedures will be annotated. PET/MRI acquisition protocol will be optimized to ensure, as much as possible, patients' compliance.

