14.4. AE Attribution Scale

RELATIONSHIP	ATTRIBUTION	DESCRIPTION
Unrelated to investigational agent/intervention	Unrelated	The AE is clearly NOT related to the intervention.
	Unlikely	The AE is doubtfully related to the intervention.
Related to investigational agent/intervention	Possible	The AE may be related to the intervention.
	Probable	The AE is likely related to the intervention.
	Definite	The AE is clearly related to the intervention.
Reference: NCI Guidelines: Adverse Event Reporting Requirements		

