14.5. Procedures for Reporting Adverse Events

All AEs occurring during the safety window for the trial as defined above that are observed by the Investigator or reported by the participant will be reported in the trial CRF.

The following information will be reported in the CRF: description, date of onset and end date, severity, assessment of relatedness to trial medication, other suspect drug or device and action taken. Follow-up information should be provided as necessary.

The severity of events will be assessed on the following scale: 1 = mild, 2 = moderate, 3 = severe. Non-serious AEs considered related to the trial medication as judged by a medically qualified investigator will be followed up either until resolution or until the event is considered stable.

It will be left to the Investigator's clinical judgment to decide whether or not an AE is of sufficient severity to require the participant's removal from treatment. A participant may also voluntarily withdraw from treatment due to what he or she perceives as an intolerable AE. If either of these occurs, the participant must undergo an end of trial assessment and be given appropriate care under medical supervision until symptoms cease, or the condition becomes stable.

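### The only named safety criterion, patient compliance, carries no information on harm; no adverse-event summary is planned, and the CRF relatedness item gives the biopsy no category

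*Combined protocol and SAP*

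**What the plan says.** - **Criterion.** In the protocol synopsis, the entry beside "Safety Criteria" is "Patients' compliance".
- **Definition of compliance (10.7).** "All patients that will complete PET/MRI examination and will undergo prostate biopsy will be considered compliant with the clinical trial". No adverse event enters this definition.
- **Section 7.2.** It opens "A large amount of evidence shows that ¹⁸F-PSMA is well tolerated" and goes on to drug reactions and exclusions. It names no safety measure and does not mention the biopsy.
- **Section 16.** It contains no safety summary and no safety population.
- **Attribution.** The related category of the 14.4 scale is "Related to investigational agent/intervention". The synopsis lists "Prostate biopsy guided by imaging findings" among the interventions, although section 10.12 (Other Interventions) is marked not applicable. The CRF items in 14.5 are "assessment of relatedness to trial medication, other suspect drug or device and action taken".
- **Severity.** Section 14.3 uses five grades, up to life-threatening and death. Section 14.5 uses three: mild, moderate, severe.
- **Follow-up of events.** Section 14.5 speaks of non-serious events judged related to trial medication. Section 14.7 speaks of any event.
- **Window.** Section 14.5 refers back to a safety window that no earlier section defines. The schedule in section 11 gives the biopsy visit and the final visit the same nominal day and tolerance (+90 ± 90), and the synopsis says no visits follow the biopsy.

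**The concern.** A safety criterion should change when patients are harmed. This one does not: a man admitted to hospital with a biopsy complication is as compliant as a man with no event. If the trial reports safety as the synopsis defines it, the result is a completion rate.

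The gap matters most for the biopsy. Section 10.6 describes systematic plus MRI-targeted biopsy as the usual procedure and adds four PET-targeted cores per PET region. Section 8 cites avoidance of biopsy side effects as a benefit of the approach. Biopsy harm is therefore part of the rationale, yet the plan contains no summary of it and the CRF item does not name it as a possible cause. Two investigators recording the same post-biopsy bleed could code it differently, depending on whether they follow 14.4 or 14.5.

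**Working it through.** **1. The plan's own figure.** The documents state no safety figure. The one sample-size figure (section 16.2) concerns sensitivity: assumed sensitivity 0.96, precision ±0.04, 95% confidence, prevalence 0.56.

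- Men with csPCa: 1.96² × 0.96 × 0.04 / 0.04² = 92.2, rounded up to 93.
- Total: 93 / 0.56 = 166.1, rounded up to 167. This reproduces the plan.

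So 167 was not chosen with safety in mind, and no complication rate, safety margin or dropout allowance is given.

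**2. What the criterion can register.** Compliance (10.7) = PET/MRI completed and biopsy done. Take two men with both steps completed, one with a serious biopsy complication and one without. Both are compliant, so the measure cannot tell them apart.

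**3. Section 14 side by side.**

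| Item | One section | Another section | Result |
|---|---|---|---|
| Relatedness | 14.4: agent or intervention | 14.5: trial medication; other suspect drug or device | Biopsy falls within the first and is not named in the second |
| Severity | 14.3: grades 1–5 | 14.5: grades 1–3 | Grades 4 and 5 have no place on the 14.5 scale |
| Events followed | 14.5: related non-serious AEs | 14.7: any event | Different scope |
| Window | 14.5: as defined earlier | No definition found | Collection period unknown |

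**4. What a table of events would give.** With zero events in n men, the exact two-sided 95% upper limit is 1 − 0.025^(1/n). Section 16.1 specifies two-sided intervals.

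- n = 167: 1 − 0.025^(1/167) = 2.2%.
- n = 125 (assumed, to show the effect of fewer evaluable men): 2.9%.

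The chance of seeing at least one event in 167 men is 1 − (1 − p)^167. At assumed true rates of 0.5%, 1% and 2% this is 57%, 81% and 97%.

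**5. Could the table isolate the PET-targeted cores?** Compare men without PET-targeted cores (n₁, rate p₁) and with them (n₂, rate p₂). All rates and shares here are assumptions. At two-sided 5%, approximate power = Φ[(|p₂ − p₁| − 1.96·se₀)/se₁], with se₀ from the pooled rate and se₁ from the separate rates.

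- Highest case, 30% PET-positive, 5% versus 10%: n₁ = 117, n₂ = 50, se₀ = 0.0416, se₁ = 0.0470; power = Φ(−0.67) = 25%.
- Lowest case, 70% PET-positive, 1% versus 2%: n₁ = 50, n₂ = 117, se₀ = 0.0218, se₁ = 0.0191; power = Φ(−1.72) = 4%.

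The normal approximation is rough at such rates, but the conclusion does not depend on the second digit. The groups are also defined by PET result, not by randomisation.

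**The case against.** The strongest reply is that harm is captured whatever the synopsis says. An AE counts whether or not it is product-related (14.2). Events are assessed at the biopsy and final visits (section 11). SAEs go on a dedicated form (14) and are communicated within 24 hours (14.6). The CRF holds a description and dates, so post-biopsy events can be picked out afterwards. Section 5.1 names compliance as a potential risk of the long scan, which explains the synopsis entry. All of this stands, and it limits the point to definition, attribution and planned reporting.

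It also rules out several stronger readings that a reader might infer:

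- *A man with a serious biopsy complication scores as a safety success.* The protocol has no safety score or pass/fail rule. He counts as compliant, and his event is still recorded and reported.
- *Relatedness is rated for the tracer only, so biopsy events must be coded unrelated.* Section 14.5 also lists another suspect drug or device, and 14.4 is wider. The documents conflict on scope and do not instruct that coding.
- *Section 14.5 restricts follow-up to related events.* It says those will be followed, not that others will not. The two sections differ and need reconciling.
- *Biopsy harm cannot be shown.* Overall biopsy harm can be described from the records. The increment from PET-targeted cores cannot be isolated, mainly because the trial is single-arm and every man has systematic cores. Better CRF wording would not change that.
- *Section 5.3 rests the trial on low biopsy risk.* It discusses scan time and radiation, and argues that the low risk is justified by the potential benefit.

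**Conclusion.** The concern holds as a defect of definition and planned reporting, and should be corrected. The sole named safety criterion is a completion measure, no AE summary is planned, the CRF relatedness item omits a listed intervention, and section 14 is inconsistent on attribution, severity grades and the events followed, with an undefined collection window. This rests on the text and needs no assumption.

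In size, a tabulation would allow a statement such as an upper limit of about 2.2% if no related SAE occurred. That assumes all 167 men are evaluable and that events are fully captured; the limit is wider with fewer men. The present criterion allows no such statement. No complication rate is given in the documents, so nothing is claimed about how much harm to expect. Nor would a table support a claim about PET-targeted cores: power to detect a doubling is about 4% to 25% under the assumed rates, in a non-randomised comparison.

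**What to change.** 1. **Synopsis and 7.2.** Replace compliance with the number and percentage of men with at least one AE and at least one SAE, by severity and relatedness, with two-sided 95% confidence intervals. Report compliance separately, as feasibility.
2. **14.5.** Align the relatedness field with 14.4 by rating tracer, MRI contrast and biopsy separately.
3. **16.1.** Add one descriptive safety table and state its denominator. It may be split by biopsy type, which follows from PET and mpMRI status, so no extra flag is needed. State that the split is descriptive and does not estimate the effect of PET-targeted cores.
4. **Section 14.** Reconcile 14.3 with 14.5 on grades, 14.4 with 14.5 on attribution, and 14.5 with 14.7 on which events are followed. Define the safety window that 14.5 cites. The content of the follow-up rule and the length of the window are for the sponsor to decide; the text should state one version. Section 10.12 should agree with the synopsis on whether the biopsy is an intervention.

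The cost is wording changes, a few CRF fields and one table, using events that are already collected. The sample size and the diagnostic-accuracy analyses are unaffected.
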